4.7.2 Descriptive Analyses

The duration of study exposure will be summarized. Summary statistics of the duration of treatment exposure in days and in subject-years will be reported by treatment group for the induction, maintenance/escalation and overall periods. The treatment exposure of the response assessment/dose hold period will be described with the number of subjects who have dose withheld and with summary statistics of the duration of the dose being withheld and of the total duration of the dose being withheld since the last dose of M1095.

The frequency of treatment exposure and the amount/dose of treatment will be provided at each visit and overall for each treatment period. The percentage of the scheduled dose will be reported for the induction, maintenance/escalation and overall periods.

All descriptive analyses on treatment compliance will be also summarized for the three treatment periods and for the overall study. The number and proportion of subjects having received the complete dose administered will be presented by each dose administered and overall by treatment group. Proportions of subjects compliant and non-compliant with study drug will be summarized by treatment group.

Data for study drug administration will be listed by treatment group and subject.

4.8 Previous and Concomitant Therapy

Data of previous and concomitant therapies will be summarized in the ITT Population.

Prior and concomitant therapies will be coded according to World Health Organization Drug Dictionary (WHO-DD version of March 2018). Prior therapies are defined as all therapies that ended prior to randomization at Week 0. Concomitant therapies are all medications:

- that started or continued on the day of or after randomization for the induction period and the overall period (from Week 0 to 52),
- or that started or continued on the day of or after the first dose of study drug of the considered period i.e.:
 - at Week 12 for the maintenance/escalation period,
 - at Week 24 for the response assessment/dose hold period.

In case of missing start and end dates, the medication will be considered as concomitant medication for the whole duration of study. If either the start date or the end date is missing or both dates are incomplete, the available information about the data will be used to infer from the randomization date/time if the therapy was taken prior to randomization or concomitantly:

- If the end date is missing and:
 - the start date is available and complete and:
 - after or on the day of randomization, the medication will be considered as concomitant,
 - prior to randomization, the medication will be regarded as concomitant therapy.
 - the start date is partial and:
 - the partial part of the start date is after the randomization date, the medication will be inferred as concomitant,
 - the partial part of the start date is prior to or the same as the comparable part of the randomization date, the medication will be concomitant medication.
- If the start date is missing and:

- the end date is available and complete and:
 - on the day of or after randomization, the medication will be considered as concomitant,
 - prior to randomization, the medication will be inferred as a prior therapy.
- the end date is partial and:
 - the partial part of the end date is the same as or after the comparable part of the randomization date, the medication will be concomitant,
 - the partial part of the end date is prior to the comparable part of the randomization date, this medication will be regarded as previous.
- If both start and end dates are incomplete,
 - If the partial part of the end date is before randomization, the medication will be classified as prior,
 - If the partial part of the start date is the same as or after the comparable part of the randomization date, the medication will be classified as concomitant.

The same rules will apply for the other treatment periods, but using the first dose of study drug of the considered period as the reference date.

The number and percentage of subjects taking previous medications and previous psoriasis medications will be summarized by treatment group, Anatomical Therapeutic Class (ATC) and preferred name. Similarly, the concomitant medications will be summarized by treatment group, by ATC and preferred name for the induction period separately and for the study overall.

Previous and concomitant therapies will be listed by treatment group and subject. The therapies will be listed with dose, unit, frequency, route of administration (if applicable), indication, start and end dates and the ongoing status.

A listing of any new treatments for psoriasis in subjects who early discontinued will be produced by treatment group and subject.

4.9 Safety and Tolerability Data

Safety data will be summarized in the Safety Population by actual treatment group.

Unless indicated otherwise, safety variables will be summarized separately for the induction period (Week 0 to 12) and the overall study (Week 0 to Week 52) per actual treatment group (refer to Table 4.2 and Table 4.3 for details about defining actual treatment groups). Overall study corresponds to the time interval from Week 0 to Week 52 for the subjects who completed the study or from Week 0 to the last follow-up for subjects who discontinued. Please note that for the overall safety analyses, the baseline for subjects who were randomized to placebo will be the last non-missing assessment before the first dose of M1095.

No formal statistical treatment comparisons of the safety data are planned.

Further safety analyses may be conducted for the overall period, maintenance/escalation and response assessment/dose hold periods as described in

Table 4.13, Table 4.14 and Table 4.15 after assessment of safety data and if deemed necessary or if indicated otherwise in this section.

Table 4.13: Actual Treatment Groups and their Labels for Pooled Safety Analyses of the Overall Period

Actual Treatment Group*	Treatment Label
	Overall (Week 0-52) Per actual received doses
(1) - (Placebo at Week 0, 1, 2, 3, 4, 6, 8 and) M1095 120 mg at Week 12, 14, 16 and Q4W	Plac/120mg (x4), Q4 ^a
(6) - Secukinumab 300 mg at Week 0, 1, 2, 3, 4, 8 (and 12 and Q4W)	Secukinumab
(2a) - M1095 30 mg at Week 0, 2, 4, 8 and Q4W if no escalation at Week 12	30mg (x4), Q4 ^b
(2b) - M1095 120 mg Q4W from Week 12 if escalation at Week 12	Presented separately
(3a) - M1095 60 mg at Week 0, 2, 4, 8 and Q4W if no escalation at Week 12	60mg (x4), Q4 ^c
(3b) - M1095 120 mg Q4W from Week 12 if escalation at Week 12	Presented separately
(4) - M1095 120 mg at Week 0, 2, 4, 8 (and 12 and Q8W)	120mg (x4), Q8
(5) - M1095 120 mg Q2W at Week 0, 2, 4, 6, 8, 10 (and 12 and Q4W)	120mg (x6), Q4
	Total 120 mg ^d
	Total M1095 ^e

*: For (2a), (3a), (4), (5) and (6), subjects will be assigned to a treatment group based on the actual treatment they received most.

a: Plac/120mg (x4), Q4 include all subjects who were mostly administered M1095 120 mg from Week 12 to Week 44 having received placebo during the induction period. The data will only be presented from Week 12 for this treatment group.

b: 30mg (x4), Q4 include the data of:

- all subjects who did not escalate and who were mostly administered M1095 30 mg during the overall period
- all subjects who escalated at Week 12 from Week 0 to Week 12 only and who mostly received M1095 30 mg during the induction period.

c: 60mg (x4), Q4 include the data of:

- all subjects who did not escalate and who were mostly administered M1095 60 mg during the overall period
- all subjects who escalated at Week 12 from Week 0 to Week 12 only and who mostly received M1095 60 mg during the induction period.

d: Total 120 mg will include the subjects who mostly received M1095 120 mg i.e. the following treatments: (1), (4), (5), (2b) and (3b). For (1), (2b) and (3b), only data from Week 12 of subjects who escalated to M1095 120 mg from Week 12 after receiving placebo, M1095 30 mg or 60 mg in the induction period will be included.

e: Total M1095 will include all subjects who received M1095 at any time during the study i.e. (1), (2a), (2b), (3), (4) and (5).

Table 4.14: Actual Treatment Groups and their Labels for Safety Analyses of the Maintenance/Escalation Period

	Dose Escalation due to IGA > 1 at Week 12?	Treatment Label	
		Maintenance/Escalation Period	Response Assessment/Dose Hold Period
Actual Treatment Group*		12	24 52 (in weeks)
(2) - M1095 30 mg at Week 0, 2, 4, 8 (and: (2a) Q4W if no escalation at Week 12)	No		
(2b) M1095 120 mg Q4W if escalation at Week 12)	Yes	30mg (x4), Q4/ Esc to 120mg	30mg (x4), Q4/ Esc to 120mg
(3) - M1095 60 mg at Week 0, 2, 4, 8 (and: (3a) Q4W if no escalation at Week 12)	No		
(3b) M1095 120 mg Q4W if escalation at Week 12)	Yes	60mg (x4), Q4/ Esc to 120mg	60mg (x4), Q4/ Esc to 120mg

*: Subjects will be assigned to a treatment group based on the actual treatment they received most during the induction and maintenance/escalation periods.

Note: Rows in grey will not be presented in tables.

Table 4.15: Actual Treatment Groups and their Labels for Safety Analyses of the Response Assessment/Dose Hold Period

	IGA = 0 at Week 24?	Treatment Label
		Response Assessment/ Dose Hold Period (Week 24-52)
Actual Treatment Group*		
(1) - Placebo at Week 0, 1, 2, 3, 4, 6, 8 (and: (1.i) M1095 120 mg at Week 12, 14, 16, 20 and dose hold from Week 24)	Yes	Plac/120mg (x4), Q4/Hold
(1.j) M1095 120 mg at Week 12, 14, 16 and Q4W	No	Plac/120mg (x4), Q4/No Hold
(6) - Secukinumab 300 mg at Week 0, 1, 2, 3, 4, 8 (and 12 and Q4W)	N/A	
(2) - M1095 30 mg at Week 0, 2, 4, 8 (and: (2a.i) Q4W and dose hold from Week 24)	Yes	30mg (x4), Q4/No Esc/Hold
(2a.j) Q4W)	No	30mg (x4), Q4/No Esc/No Hold
(2b) M1095 120 mg Q4W if escalation at Week 12)	N/A	
(3) - M1095 60 mg at Week 0, 2, 4, 8 (and: (3a.i) Q4W and dose hold from Week 24)	Yes	60mg (x4), Q4/No Esc/Hold
(3a.j) Q4W)	No	60mg (x4), Q4/No Esc/No Hold
(3b) M1095 120 mg Q4W if escalation at Week 12)	N/A	
(4) - M1095 120 mg at Week 0, 2, 4, 8 (and: (4.i) 12 and Q8W)	Yes	120mg (x4), Q8/Hold
(4.j) 12 and Q8W and dose hold from Week 24)	No	120mg (x4), Q8/No Hold
(5) - M1095 120 mg Q2W at Week 0, 2, 4, 6, 8, 10: (5.i) 12 and Q4W and dose hold from Week 24)	Yes	120mg (x6), Q4/Hold
(5.j) 12 and Q4W	No	120mg (x6), Q4/No Hold

*: Subjects will be assigned to a treatment group based on the actual treatment they received most during the induction, maintenance/escalation and response assessment/dose hold periods.

Note: Rows in grey will not be presented in tables.

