### **6.6.2 Week 24**

Any subjects on M1095 who did not undergo dose escalation at Week 12 and who achieve an IGA score of 0 at Week 24 will have study drug withheld and will receive placebo q4w.

Subsequently, if IGA score is 1 or more, these subjects will re-commence M1095 at the dose they received prior to Week 24 on a q4w regimen at the visits scheduled by the protocol until the end of the treatment period. Dose will not be withheld for a second time, irrespective of subsequent IGA scores.

At Week 24, subjects on secukinumab will continue to be treated q4w.

Site personnel will enter the IGA score into the IRT prior to the study drug kit being assigned at Week 24, 28, 32, 36, 40 and 44.

At Week 24, the investigator should carefully consider the subject's response and if there has been a worsening of psoriasis compared to baseline then the investigator should consider discontinuing the subject from the study if they are not receiving adequate benefit from their participation.

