## 9.3 Populations for Analyses

For purposes of analysis, the following populations are defined:

Population	Description
Enrolled	All subjects who sign informed consent
Intent to Treat (ITT)	The Intent to Treat (ITT) population includes all subjects randomly allocated to a treatment. Subjects will be analyzed according to planned treatment.
Modified Intent To Treat (MITT)	The Modified Intent to Treat (MITT) population includes all subjects in the ITT Analysis Set who receive at least one dose of study drug, have a baseline, and at least one post baseline efficacy assessments. Subjects will be analyzed according to planned treatment.
Per-Protocol (PP)	The Per-Protocol (PP) population includes all subjects in the MITT Analysis Set who have no important clinical protocol deviations affecting the assessment of efficacy. Membership of the PP Analysis Set will be confirmed prior to unblinding the data. Subjects will be analyzed according to planned treatment.

Safety	The Safety population includes all subjects who receive at least one dose of study treatment. The Safety population will be analyzed per the actual treatment received.
Pharmacokinetic	The Pharmacokinetic (PK) population includes all subjects who receive at least one dose of M1095 with valid (i.e. not flagged for exclusion) PK data and no protocol deviation with an impact on PK. The PK population will be analyzed per the actual treatment received.

The primary analysis set for efficacy data will be the ITT Analysis Set.

The primary analysis will be repeated on the MITT and PP Analysis Sets. Furthermore, selected sensitivity analyses will be performed on the ITT Analysis Set, including multiple imputation and last-observation carried forward. Safety data will be analyzed using the Safety Analysis Set.

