4.2.3.2.1 Variables

The post-Week 24 exploratory objectives will be explored with these variables:

Endpoints	Type of Variables	Exploratory Variables
IGA-derived endpoints	Binary	
 proportion of subjects with an IGA response at all visits from Week 24. proportion of subjects with a complete IGA response at all visits from Week 24. proportion of subjects requiring M1095 restart after withholding study drug at each visit from Week 24. cumulative proportion of subjects with M1095 restarted after withholding study drug at each visit from Week 24.
	Categorical	
 shift from Week 24 in IGA score category at all post-Week 24 visits.
	Time-to-Event	
 time to first IGA ≥ 1. time from M1095 restart to first complete IGA response during Week 24-48 interval.
PASI-derived endpoints	Binary	
 proportion of subjects achieving PASI 75/PASI 90/PASI 100 response at all visits from Week 24. proportion of subjects achieving PASI 75/PASI 90/PASI 100 response by visit during the M1095 dose hold interval. proportion of subjects achieving PASI 75/PASI 90/PASI 100 response at all visits after M1095 restart.
	Continuous	
 raw PASI score at all visits from Week 24. absolute change and percent change from baseline in PASI score at all visits from Week 24. absolute change and percent change from Week 24 in PASI score at all visits from Week 24. raw PASI score by visit during the M1095 dose hold interval. raw PASI score at all visits after M1095 restart. raw PASI score after M1095 restart as a function of time in weeks.

Table 4.9: Exploratory Endpoints and Variables Related to Post-Week 24 Dose Hold/Restart Analyses

Missing continuous or categorical variables will not be imputed. Time-to event data will be censored at the last assessment visit if the event had not occurred up to that point.

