 - If the partial or complete start and end dates do not indicate as to when the AE started and ended compared to the first dose of study drug of any period, the AE will be flagged on-treatment for all periods.
- If both start and end dates are both missing: the AE will be considered on-treatment and therefore a TEAE for all periods.

To determine the worsening of an AE during study treatment, the maximum severity for each AE during the baseline period will be considered. In case of missing severity, the conservative approach below will be followed:

- If an AE has a missing severity during the study treatment, it will be defined as treatment-emergent.

- If the severity of an AE is missing at baseline and this event continues during the study treatment, this AE will be considered as treatment-emergent.

Adverse events of Special Interest (AESI) include cytopenias, liver function test changes/enzyme elevations, infections, injection-site reactions, allergic/hypersensitivity reactions, cerebrocardiovascular events, malignancies, depression, Crohn's disease and ulcerative colitis. Additional adverse events may be identified as being of special interest during the study and prior to first unblinding.

An overview table will present the number and percentage of subjects experiencing these types of AEs below by treatment:

- TEAEs,
- TEAEs by relationship to investigational product,
- serious TEAEs including deaths,
- TEAEs by maximum severity,
- deaths,
- and TEAEs leading to study treatment discontinuation.

This table will be produced for all separate treatment periods and the overall periods (refer to Table 4.3, Table 4.13, Table 4.14 and Table 4.15).

For the overall period, the exposure-adjusted incidence per 100 subject-years will also be presented. The exposure-adjusted incidence will be calculated by dividing the number of subjects with AEs by the total person years of exposure during the treatment period (refer to Section 4.7). This result will be multiplied by 100 to obtain the exposure-adjusted incidence per 100 subject-years.

The AESI will also be displayed with an overview table by treatment for each treatment period and the overall periods.

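### The dose-hold safety tables keep held subjects in one Hold column to Week 52, so the planned AE and AESI overviews do not separate events on placebo from events after M1095 is restarted

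*SAP*

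**What the plan says.** Protocol 6.6.2 and SAP 1.4 describe the hold. A non-escalated M1095 subject with IGA 0 at Week 24 goes onto placebo. If IGA is later 1 or more, "these subjects will re-commence M1095 at the dose they received prior to Week 24 on a q4w regimen", with no second hold.

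SAP Table 4.15 sets the safety groups for this period. The column is marked "Dose Hold Period (Week 24-52", the row turns on whether IGA was 0 at Week 24, and the only labels are Hold and No Hold, for example "30mg (x4), Q4/No Esc/Hold". The Arm 1 Hold row reads "M1095 120 mg at Week 12, 14, 16, 20 and dose hold from Week 24" and does not mention a restart. A footnote assigns subjects to groups "based on the actual treatment they received most during the induction, maintenance/escalation and response assessment/dose hold periods".

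SAP 4.9.2.5 counts an event in a period if it emerges or worsens between the first administration of that period and its last visit. Subjects who discontinue have their own cut-off, but a restart does not create one. Of the AE overview the SAP says "This table will be produced for all separate treatment periods and the overall periods", with Table 4.15 among the tables cited. An AESI overview is also planned for each period.

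Protocol 9.3 states the general principle: "The Safety population will be analyzed per the actual treatment received".

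**The concern.** A held subject can have two different exposures under one label: placebo until the first visit with IGA 1 or more, then M1095 again up to Week 44. An injection-site or hypersensitivity reaction after the restart dose, and one that occurs during placebo, fall in the same column. Both are listed as AESIs, and re-exposure after a gap is where a reader would look for them.

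The SAP makes comparable cuts elsewhere. For efficacy, Table 4.9 has separate variables for the hold interval and for the time afterwards, such as "raw PASI score at all visits after M1095 restart". For pooled safety, Table 4.13 (footnotes b to d) cuts escalated subjects at Week 12, so that their data follow the dose being received. Nothing similar happens at the restart.

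In Arm 4 the label is also inexact. The restart is every 4 weeks, but the subject stays under a heading that names the 8-weekly regimen.

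**Working it through.** **Check against a stated figure.** SAP 1.4 limits placebo after Week 24 to 20 weeks. The last dose is at Week 44 (Protocol 6.7), and 44 − 24 = 20, so the visit arithmetic agrees.

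**Inputs.** The Table 4.15 window is Week 24 to 52: 52 − 24 = 28 weeks. The hold starts at Week 24. IGA is entered before kit assignment at Weeks 24, 28, 32, 36, 40 and 44 (Protocol 6.6.2), so a restart can fall at Week 28, 32, 36, 40 or 44. The SAP's washout is 56 days (4.7.1). In Table 4.12, d is the number of days from the Week 20 dose to restart, and d1 = d − 56, set to 0 if negative.

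**Formulas for a restart at Week r.** Hold weeks = r − 24. Weeks after restart = 52 − r. Share after restart = (52 − r)/28. d = (r − 20) × 7.

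| Restart | Hold weeks | Weeks after | Share after | Placebo / M1095 occasions, Weeks 24–44 | d (days) | d1 (days) |
|---|---|---|---|---|---|---|
| Week 28 | 4 | 24 | 86% | 1 / 5 | 56 | 0 |
| Week 32 | 8 | 20 | 71% | 2 / 4 | 84 | 28 |
| Week 36 | 12 | 16 | 57% | 3 / 3 | 112 | 56 |
| Week 40 | 16 | 12 | 43% | 4 / 2 | 140 | 84 |
| Week 44 | 20 | 8 | 29% | 5 / 1 | 168 | 112 |
| Never | 28 | 0 | 0% | 6 / 0 | – | – |

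A subject with one placebo and five M1095 dosing occasions in the period therefore shares a column with a subject who had six placebo and none of M1095.

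**What fixes the label.** It is the IGA condition at Week 24 together with the Week 24–52 header. The footnote on treatment received most cannot do it:

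- A never-restarted subject in Arm 2 or 3 has M1095 at Weeks 0, 2, 4, 8, 12, 16 and 20 (7 occasions). Placebo is given at Weeks 1, 3, 6, 10 and 14 and at six visits from Week 24 (5 + 6 = 11).
- An Arm 1 subject restarting at Week 28 has 8 + 1 = 9 placebo occasions and 4 + 5 = 9 of M1095, a tie.

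A majority rule over all three periods does not separate Hold from No Hold. On any reading of it, hold time and time after restart stay in one column.

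**Row text.** In Table 4.15, row (4.i) is marked as IGA 0 and Hold but its regimen text has no hold. Row (4.j) is marked No Hold but its text includes one. Table 4.12 puts the hold on (4.i), so the text in Table 4.15 appears swapped.

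**The case against.** The strongest reply is that this is one descriptive table in a phase 2b trial. No formal safety comparison is planned (SAP 4.9). Protocol 9.4.5 asks for AEs by treatment period, and the SAP follows it. Efficacy also uses Hold and No Hold groups (Table 4.10); Table 4.9 adds variables, not groups. SAP 4.9 makes further analyses on Table 4.15 conditional. The last argument does not cover the AE and AESI overviews, which 4.9.2.5 plans outright. The others limit the weight of the point but do not supply the missing split.

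Some stronger readings are tempting and are not supported:

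- A reader might infer that the trial cannot show whether events occur on re-exposure. AE data and drug administration are both listed by subject (SAP 4.9.2.5 and 4.7.2), so a split could be rebuilt. What is missing is a planned summary.
- A reader might equate the hold interval with time off drug. With a Week 28 restart, d1 = 0 under the SAP's own washout. In Arm 4, 8-weekly dosing from Week 12 gives M1095 at Weeks 20 and 28 and placebo at Week 24, so a Week 28 restart creates no gap relative to the unheld schedule.
- A reader might infer that the Hold column is mostly M1095 time. Without a restart distribution, the share after restart can lie anywhere from 0% to 86%.
- A reader might derive a headcount from the 45 to 72% PASI 100 range in the sample-size section. That range is for Week 12 and a different endpoint. It takes no account of escalated subjects, who cannot be held, and subjects who never restart have nothing pooled.
- A reader might argue from anti-drug antibodies. Their analysis is in a separate plan (SAP 4.11) that is not available here.

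**Conclusion.** The point holds as a gap in the planned safety summaries. For Weeks 24 to 52, the AE and AESI overviews pool placebo-interval and post-restart events for every Hold group, and no other planned safety summary separates them. For a subject who restarts, between 29% and 86% of the window follows the restart, depending on the visit; for one who does not, none does. These shares assume restart at a scheduled visit and follow-up to Week 52. The number of subjects affected cannot be derived from the documents.

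The efficacy conclusions are untouched and no data are lost. Prespecifying the split is still better than rebuilding it from listings after unblinding, and the SAP already relies on the restart date for Tables 4.9 and 4.12. This is a cheap improvement that should be made.

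**What to change.** In the AE and AESI overviews for this period, split each Hold group (Arms 1 to 5, non-escalated subjects in Arms 2 and 3) at the first restart dose:

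- hold interval: Week 24 to restart, or to the end of follow-up if M1095 is never restarted;
- after restart: restart to Week 52.

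Assign each treatment-emergent event by onset date and show subject-years for each part. SAP 4.7.2 reports subject-years for induction, maintenance/escalation and overall only, so the time at risk for these two parts needs a short definition. The combined column may be kept alongside.

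Do not label the hold interval off drug. If an off-drug summary is wanted, count it from 56 days after the last M1095 dose, in line with Table 4.12.

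In the same amendment, replace the Table 4.15 footnote with a rule that defines Hold and No Hold, and reconcile the text of rows (4.i) and (4.j).

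The cost is a change to table shells and a date split, with no new data collection. The drawback is smaller columns, with subjects who restart appearing in two of them.
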